10.1.5 Adherence to study medication over time

Endpoints

Adherence during the trial will be monitored by subject questioning regarding missed tablets at each visit. Compliance rate for each participant will be estimated by the response of the following item: Thinking about the last week, how often has the subject taken their medication? The response is classified in 5 categories (All the time, Most of the time, About half of the time, Very few times, None).

Descriptive statistics and graphical representation

Analyses will be performed with the mITT population for which data are available at each time point. The data will be summarized by the number and percentage of participants per class at each time point. A bar chart will be presented.

Statistical methodology

The analysis will be descriptive and no inference will be made.

10.1.6 Change from baseline in plasma and urine laboratory parameters

Endpoints

The endpoints are the change from baseline plasma and urine laboratory parameters

Descriptive statistics and graphical representation

The analyses will be performed with the mITT population and DSP1.

Data will be summarised by mean and standard error. The evolution will be described by boxplots for each treatment group at each time point.

Statistical methodology

The changes from baseline in haematology, chemistry, lipid and glycaemia will be compared between the two treatment groups using mixed models for repeated measures with random intercept and slope and spatial power covariance structure due to unequal time intervals between visits, adjusted for country/group of neighbouring countries and baseline CD4 cell counts (<50 or $\geq 50/\mu\text{L}$). The model will include treatment group, time, interaction between treatment group and time, country/group of neighbouring countries and baseline CD4 cell counts (<50 or $\geq 50/\mu\text{L}$). Time will be modelled as categorical variables.

All p-values will be two-tailed, with a significant level of 0.05.

10.2 EXPLANATORY ENDPOINTS

10.2.1 Mutations detected by deep sequencing compared with those detected by population sequencing

Endpoint

The endpoint is the proportion of patients for whom there is a difference in the list of mutations (Stanford list last available version) detected by deep sequencing compared with those detected by population sequencing.

Descriptive statistics and graphical representation

The analyses will be performed with the mITT population and DPS1. Data will be summarized with the number and percentage of participants with difference in the list of mutations detected by deep sequencing compared with those detected by population sequencing.

Statistical methodology

The proportion of patients with difference in the list of mutations detected by deep sequencing compared with those detected by population sequencing will be estimated by dividing the number of participants with difference in the list of mutations detected by deep sequencing compared with those detected by population sequencing by the total number of participants in the mITT population.

The effect of study treatment on the proportion patients with difference in the list of mutations detected by deep sequencing compared with those detected by population sequencing will be assessed using a logistic regression model with treatment group and adjustments for stratification factor (country/group of neighbouring countries and baseline CD4 cell counts (<50 or \geq 50/ μ L)). An adjusted odds ratio (OR) and the associated 95% Confidence Interval (CI) will be calculated.

10.2.2 Proportion of patients with HIV RNA viral load <50 copies/mL at week 4, 8, and 12

Endpoint

The endpoint is the proportion of patients with HIV-RNA viral load <50 copies/mL at week 4, 8 and 12 using the snapshot approach.

Virologic outcome will be determined by the last available measurement while the participant is on treatment and continues on trial within the time window. The time window for each timepoint is defined in Table B below.

Table B: Proposed Windows

Visit	Window (Through End-of-Study Week)	Window (Days)
4	2-6	15-42
8	6-10	43-70
12	10-14	71-98

Descriptive statistics and graphical representation

The analyses will be performed with the mITT population and DPS1. Data will be summarized with the number and percentage of participants with an event.

Statistical methodology

The proportion of patients with HIV-RNA viral load <50 copies/mL will be estimated by dividing the number of participants with HIV-RNA viral load <50 copies/mL by the total number of participants in the mITT population.

The effect of study treatment on the proportion patients with HIV-RNA viral load <50 copies/ml at week 4, 8, and 12 will be assessed using a logistic regression model with treatment group and adjustments for stratification factor (country/group of neighbouring countries and baseline CD4 cell counts (<50 or \geq 50/ μ L)). An adjusted odds ratio (OR) and the associated 95% Confidence Interval (CI) will be calculated.

10.2.3 Evolution of HIV RNA in individuals with viral load >50 copies/mL at week 48**Endpoint**

The endpoint is the evolution of HIV RNA between week 48 and week 52 in individuals with viral load >50 copies/mL at week 48.

Descriptive statistics and graphical representation

Analyses will be performed in participants with HIV RNA viral load >50 copies/mL at week 48. Data will be summarized for each treatment group: (i) the number of participants with 50-200 HIV RNA at week 48 and a viral load increasing by >200 copies/mL, remaining at 50-200 copies/mL or decreasing to <50 copies/mL at week 52. (ii) the number of participants with >200 HIV RNA at week 48 and a viral load remaining at >200 copies/mL, decreasing to 50-200 copies/mL or decreasing to <50 copies/mL at week 52. The evolution between week 48 and 52 will be analysed graphically using trend analysis.

Statistical methodology

A descriptive analysis will be carried out and no statistical inferences will be made.

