6.6.1 Resistance testing

Next generation sequencing (deep sequencing) may be performed centrally to evaluate the significance of the HIV-1 mutations detected by this method, which are identified during standard population sequencing of the HIV viral load response.

Blood samples for these tests will be taken at the baseline visit and treatment phase visits (Week 4, 8, 12, 24, 36 and 48). A sample will be taken at the ETV for patients with virological failure identified outside of a scheduled visit.

Samples will be shipped on a periodic basis from the sites to ACM Global for central storage and shipped to Monogram Biosciences for analysis.

At the end of the study, samples taken from patients that do not have virological failure will be destroyed, either locally, or at ACM Global.

Collection, processing and storage instructions will be detailed in a separate laboratory manual.

See Appendix 1 for details of assessments required.

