14	Resistance testing for deep sequencing (sent to central laboratory)	
In addition to the resistance test performed locally, a resistance testing sample will be taken at the Baseline visit, each visit in the treatment phase (Week 4, 8, 12, 24, 36 and 48) and at the ETV (for patients with virological failure identified outside of a scheduled visit).
 
All resistance testing samples for patients with virological failure will be sent to a central laboratory for next generation sequencing to look for low-level pre-existing resistance in cases of suspected resistance development.

15	Drug dispensing	There will be four dispensations of the study medication to the patient (Baseline visit, Week 12, 24 and 36).
16	Adherence	Also performed at the ETV if required.
17	Serum pregnancy test	For women of child bearing potential only (see Appendix 7 for definition).
18	Urine pregnancy test	Dipstick and urine pregnancy test (WOCBP only - see Appendix 7 for definition). This is a mandatory assessment. If a urine pregnancy test is not possible, a serum pregnancy test can replace this.
19	Physical examination	Weight is required at all visits, as detailed in the appendix 1, however height is only required at baseline.

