2.1.3 Exploratory objectives

The exploratory objective of this study is to assess whether virologic response is better predicted by deep sequencing rather than standard population sequencing.

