3. STUDY METHODS

3.1 GENERAL STUDY DESIGN AND PLAN

LAPTOP study is an international, open-label, randomised, two arm, multicentre trial over 48 weeks to compare two strategies for HIV-1 infected patients with advanced disease.

Eligible patients will be randomised to receive either an integrated inhibitor containing regimen (B (50mg)/F (200mg)/TAF (25mg) [1 pill administered orally once daily for 48 weeks]) or a boosted PI regimen (D (800mg)/C (150mg)/F(200mg)/TAF (10mg) [1 pill administered orally once daily for 48 weeks]). Randomisation is stratified by country and baseline CD4 cell count (<50 cells/ μ L, 50-199 cells/ μ L, or \geq 200 cells/ μ L).

[figure not shown]

Figure 1: Study design

Study participants will be ART-naïve, HIV-1-infected individuals aged 18 or older who have at entry HIV viral load > 1000 copies/ml and at least one of the following: i) have AIDS with any CD4 cell count; ii) have severe bacterial infection (BI) and must have a CD4 cell count < 200/µl within 30 days prior to study entry; iii) are asymptomatic with CD4 cell count < 100/µL within 30 days prior to study entry; iv) are currently receiving treatment for OI. Women who were pregnant or breastfeeding or who declined a contraceptive method at screening were not eligible.

After the screening visit, participants will be seen at baseline, when they initiated c-ART and weeks 4, 8, 12, 24, 36 and 48, as well as a follow-up visit 30 days following the week 48 visit.

At each visit, participants will have routine safety monitoring as well as measurement of plasma HIV-1 RNA viral load, CD4, CD8 cells counts and a deep sequence resistance test. In the event of virological failure, local resistance tests should be performed on the first sample, and participants should discontinue study treatment and receive rescue therapy at the investigators' discretion.

Quality of life (QoL) questionnaire (EuroQoL EQ-5D-3L) and HIV Symptom Index (HIV-SI/SDM) questionnaire will be administrated at each visit from baseline.

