14	Resistance testing for deep sequencing (sent to central laboratory)	In addition to the resistance test performed locally, a resistance testing sample will be taken at the Baseline visit, each visit in the treatment phase (Week 4, 8, 12, 24, 36 and 48) and at the ETV (for patients with virological failure identified outside of a scheduled visit). All resistance testing samples for patients with virological failure will be sent to a central laboratory for next generation sequencing to look for low-level pre-existing resistance in cases of suspected resistance development.
15	Drug dispensing	There will be four dispensations of the study medication to the patient (Baseline visit, Week 12, 24 and 36).
16	Adherence	Also performed at the ETV if required.
17	Serum pregnancy test	For women of child bearing potential only (see Appendix 7 for definition).
18	Urine pregnancy test	Dipstick and urine pregnancy test (WOCBP only - see Appendix 7 for definition). This is a mandatory assessment. If a urine pregnancy test is not possible, a serum pregnancy test can replace this.
19	Physical examination	Weight is required at all visits, as detailed in the appendix 1, however height is only required at baseline.

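### SAP 10.2.1 divides sequencing discordance by the whole mITT population, although deep sequencing is foreseen only for virological failures, so the reported proportion is understated

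*Combined protocol and SAP*

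**What the plan says.** SAP 10.2.1 defines the outcome per patient: "The endpoint is the proportion of patients for whom there is a difference in the list of mutations", comparing deep with population sequencing. The analysis is set in the mITT population, that is, everyone randomised and dosed (SAP 5.2.1), and the count of discordant patients is divided "by the total number of participants in the mITT population". A logistic regression adjusted for the stratification factors then estimates a treatment effect on this proportion. SAP Table 8 gives the endpoint a row with adjusted odds ratio and P-value columns.

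On who is deep-sequenced, four places bear:

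- SAP 3.3, note 14: "All resistance testing samples for patients with virological failure will be sent to a central laboratory for next generation sequencing".
- Protocol v5.0, Appendix 1, note 14, has the same rule and gives the purpose as "to look for low-level pre-existing resistance in cases of suspected resistance development".
- Protocol v5.0 section 6.6.1: "Next generation sequencing (deep sequencing) may be performed centrally", and at the end of the study "samples taken from patients that do not have virological failure will be destroyed, either locally, or at ACM Global".
- SAP 3.1 points the other way. It lists, for all participants at each visit, "CD4, CD8 cells counts and a deep sequence resistance test".

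The exploratory objective (SAP 2.1.3, and protocol section 2.3 in nearly the same words) is "to assess whether virologic response is better predicted by deep sequencing rather than standard population sequencing".

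**The concern.** A difference between two methods can be observed only in a patient who was tested by both. Dividing by all mITT participants places every patient without a deep sequence in the denominator as though the methods had agreed. The result is then the product of two quantities: how many patients were sequenced, which follows the failure rate, and how often the methods disagree in them. Only the second is of interest.

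The SAP handles the parallel question differently. Section 7.2.3 divides patients with resistance mutations by the virological failures whose genotype was obtained. Section 10.2.1 departs from that practice without giving a reason.

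Two results are at stake. The headline proportion would make deep sequencing look less informative than it was. Table 8 could also show an odds ratio and P-value, presented as a treatment effect on sequencing discordance, that partly restate which arm had more failures. Separately, prediction of response needs sequences from responders as well as failures. None is planned for responders, and 10.2.1 contains no response variable.

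**Working it through.** **Design inputs.** Section 10.2.1 states no figure, so I first checked the section 4 figures used below.

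- Margin: ln(1 − 0.37)/ln(1 − 0.25) = 1.606, as stated.
- Events: 4 × (1.960 + 0.842)² / (ln 1.606 − ln 0.909)² = 96.9, so 97, as stated.
- Evaluable: 97/0.24 = 404, as stated (0.24 is the mean of 25% and 23%).
- Enrolled: 404/(1 − 0.075) = 437, against 440 planned.

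**Level of the proportion.** Let s be the fraction of the mITT population that is deep-sequenced and c the discordance among those sequenced. The reported proportion is s × c, so it cannot exceed s and is too small by a factor 1/s. SAP section 4 takes virological failure as 20% at week 48 in a darunavir arm. If every failure is sequenced, s = 0.20. The documents give no value for c. With c = 0.50 as an assumption, 0.20 × 0.50 = 0.10, a five-fold understatement (1/0.20). If fewer failures are sequenced, as the optional wording in protocol 6.6.1 allows, the factor is larger.

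**Comparison of arms, if the model keeps the mITT denominator.** Assumptions: PI virological failure 20%; INI virological failure 1 − 0.8^HR, applying the plan's hazard ratios to virological failure; the same c in both arms; 220 per arm. The columns for reported proportions and the first odds ratio use c = 0.50.

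| HR | INI failure | Sequenced, PI / INI | Reported, PI / INI | OR | OR for c = 25–100% |
|---|---|---|---|---|---|
| 0.5 | 10.6% | 44 / 23 | 10.0% / 5.3% | 0.50 | 0.47–0.52 |
| 0.909 | 18.4% | 44 / 40 | 10.0% / 9.2% | 0.91 | 0.90–0.91 |
| 1.606 | 30.1% | 44 / 66 | 10.0% / 15.1% | 1.60 | 1.55–1.72 |

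For example, at HR 0.5: (0.053/0.947)/(0.10/0.90) = 0.50. The methods disagree equally often in both arms in every row, so any departure from 1.00 comes from the failure rates. An unadjusted two-proportion comparison would reach p < 0.05 with probability 25–79% at HR 0.5 and 19–69% at HR 1.606 over this range of c.

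A real difference can also be hidden. At HR 0.5, discordance of 40% (PI) against 76% (INI) gives 0.20 × 0.40 = 8.0% and 0.106 × 0.76 = 8.0%.

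**With the denominator restricted to patients with both sequences,** each arm reports c itself, and equal discordance gives an odds ratio of 1.00 in all three rows.

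**The case against.** **Failures-only sequencing is pieced together.** Note 14 says which samples are sent but does not say that no others are. Destruction is at the end of the study, which does not exclude earlier sequencing, and SAP 3.1 reads as though everyone is tested at each visit. This stands as a call to reconcile the text. It does not remove the point: the schedule describes the visit item as sample collection, note 14 is the specific rule on what is sequenced, and a denominator of patients with both sequences is right on either reading.

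**The regression has no stated coding for unsequenced patients.** The mITT division is written for the proportion only. A logistic model would normally drop missing outcomes, and SAP sections 5 and 6 base percentages on non-missing data. The specific sentence in 10.2.1 overrides that general rule for the proportion, but the model's handling is open. The distortion of the odds ratio is therefore conditional.

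**The effect on the arm comparison may be slight.** Under the plan's composite rates of 25% and 23%, with 40% discordance assumed in both arms, the proportions are 10.0% and 9.2% and the odds ratio is (0.092/0.908)/(0.10/0.90) = 0.91, or about 1.10 inverted. This stands.

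**The endpoint is exploratory.** It cannot alter the primary conclusion. This also stands and limits the weight of the point.

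**Conclusion.** The denominator in SAP 10.2.1 is a wrong stated rule, not merely a missing detail. The understatement of discordance follows from the arithmetic and does not depend on any difference between arms. It is about five-fold at 20% virological failure with all failures sequenced. The effect on the odds ratio requires that the model use the same denominator, and its size depends on how far failure rates diverge: small at the planning hazard ratio, large at 0.5 or 1.606.

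A reader might infer that the planned odds ratio mainly reflects who failed. Taking failure of 25% against 15% and 40% discordance in each arm, for instance, gives 10% against 6% and an odds ratio of (0.10/0.90)/(0.06/0.94) = 1.74. The documents do not support that as an expected result. The 25% is the composite assumption for the PI arm and not virological failure, a contrast with 15% appears nowhere, and the model's handling of unsequenced patients is not stated.

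The objective of comparing prediction of response cannot be met by this analysis if only failures are sequenced.

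**What to change.** 1. As in SAP 7.2.3, restrict the denominator of 10.2.1 to participants with both a deep and a population sequence from the same treatment phase: a pre-treatment pair (screening or baseline) or a failure pair. Requiring the same time point would be too strict. The local test is done at screening, or the last earlier result is used, while deep-sequencing samples start at baseline, so pre-treatment pairs could be lost.
2. Report the number sequenced in each arm and describe agreement by arm.
3. Drop the mITT logistic regression and the corresponding odds ratio and P-value cells in Table 8.
4. Reconcile SAP 3.1 with note 14 and protocol 6.6.1 on who is deep-sequenced.
5. State in the SAP, with a matching note to protocol section 2.3, that the analysis addresses agreement between methods among virological failures and not prediction of response.

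No extra sequencing is needed. The SAP is version 0.3, and its section 5.1 foresees updating before sign-off. The cost is a narrower exploratory objective and a small protocol note, because the objective also appears there.

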1. REPORTING CONVENTIONS

P-values \geq 0.001 will be reported to 3 decimal places; p-values less than 0.001 will be reported as "<0.001". The mean, standard deviation, and any other statistics other than quantiles, will be reported to one decimal place greater than the original data. Quantiles, such as median, or minimum and maximum will use the same number of decimal places as the original data.

Estimated parameters, not on the same scale as raw observations (e.g. regression coefficients) will be reported to 3 significant figures.

2. STATISTICAL SOFTWARE

Statistical analyses will be performed using SAS® version 9.4 (SAS Institute Inc., Cary, NC, USA). Stata version 15.0 (StataCorp, College Station, TX, USA) will be used for graphical representation of selected analyses.

4. LISTING OF TABLES AND FIGURES

TABLE 1. BASELINE CHARACTERISTICS

	Integrase inhibitor (N=XXX)	Protease inhibitor (N=XXX)	Total (N=XXX)
Age (years), median (IQR)			
Gender			
Male			
Female			
Child bearing potential			
Ethnicity			
White caucasian			
White mixed			
Asian			
Black			
African			
Caribbean			
Other			
Prior AIDS-defining event			
No			
Yes			
Days from HIV diagnosis to treatment initiation, median (IQR)			
HIV RNA viral load, log10 copies/mL, median (IQR)			
<100,000			
100,000 – 500,000			
>500,000			
CD4+ count (cells/µL)			
<50			
50 – 199			
≥200			
CD4+ (%)			
CD8+ count (cells/µL), median (IQR)			
CD8+ (%)			
CD4/CD8 ratio, median (IQR)			
<0.10			
0.10 – 0.30			
>0.30			
Alcohol intake			
Does not drink alcohol			
Drinks alcohol			
Current Smokers			
Never smoked			
Current smoker			
Ex smoker			
Recreational drug use			
Positive HBV Antigen			
Positive HCV antibody			
HCV RNA VL, median (IQR)			
Positive TB testing result			
Body mass index (BMI, kg/m²)			
Weight, Kg			
Systolic Blood Pressure (mmHg)			
Diastolic Blood Pressure (mmHg)			
Pulse rate			
Red blood cells (10 ¹² /L)			
White blood cells (10 ¹² /L)			
Platelet counts (10 ⁹ /L)			
Haemoglobin (g/dL)			

Hematocrit (%)
MVC (fl)
MCH (pg)
Neutrophils ($10^{12}/L$)
Lymphocytes ($10^{12}/L$)
Monocytes ($10^{12}/L$)
Eosinophils ($10^{12}/L$)
Basophils ($10^{12}/L$)
Potassium (mmol/L)
Total Protein (mmol/L)
Sodium (mmol/L)
ALT (U/L)
Total Bilirubin (umol/L)
Indirect bilirubin (umol/L)
ALT (U/L) ; AST (U/L)
Albumin (g/L)
Creatinine (umol/L)
Creatinine clearance (eGFR) (mL/min)
Alkaline phosphatase (U/L)
Creatinine phosphokinase (U/L)
Calcium (mmol/L)
Urea (mmol/L)
Phosphate (mmol/L)
Chloride (mmol/L)
Fasting plasma lipids and glucose
Total cholesterol (mmol/L)
HDL-cholesterol (mmol/L)
LDL-cholesterol (mmol/L)
Triglyceride (mmol/L)
Glucose (mmol/L)

TABLE 1B: BASELINE RESISTANCE MUTATIONS

Characteristic		Integrase inhibitor (N=XXX)	Protease inhibitor (N=XXX)	Total (N=XXX)
Resistance testing, n (%)				
	No			
	Yes			
Resistance mutations to ARV class				
	NRTI			
	NNRTI			
	PI			
	INI			
NRTI mutations (Stanford algorithm last version)				
NNRTI mutations (Stanford algorithm last version)				
PI mutations (Stanford algorithm last version)				
INI mutations (Stanford algorithm last version)				
Resistance to DRV (stanford algorithm)				
	Resistance			
	Intermediate			
	Sensitive			
Resistance to BIC (stanford algorithm)				
	Resistance			
	Intermediate			
	Sensitive			
Resistance to 3TC/FTC (stanford algorithm)				
	Resistance			
	Intermediate			
	Sensitive			
Resistance to TAF (stanford algorithm)				
	Resistance			
	Intermediate			
	Sensitive			
Resistance to TDF (stanford algorithm)				
	Resistance			
	Intermediate			
	Sensitive			

TABLE 2. PRIMARY COMPOSITE ENDPOINT AND ITS COMPONENT

	mITT analysis			PP analysis		
	Integrase Inhibitor	Protease Inhibitor	Adjusted Hazard ratio	Integrase Inhibitor	Protease Inhibitor	Adjusted Hazard ratio
	N=XXX	N=XXX		N=XXX	N=XXX	
Primary composite endpoint						
Virological failure						
Insufficient virological response						
Viral rebound						
Clinical events						
Any new or recurrent AIDS defining event on, or after 28 days of therapy						
SAE due to Non-AIDS events						
AE leading to discontinuation						
Death						

Insufficient virologic response: (HIV-1 RNA reduction < 1 log 10 copies/mL at week 12, or Viral load > 50 HIV-1 RNA copies/mL at week 48).

Viral rebound: confirmed rebound of HIV-1 RNA to >200 copies/mL after having achieved HIV-1 RNA <50 copies/mL, or confirmed rebound of HIV RNA by >1 log 10 copies/mL from nadir value, for patients whose viral load has never been suppressed below 50 copies/mL.

TABLE 2B. CUMULATIVE INCIDENCE OF THE PRIMARY COMPOSITE ENDPOINT

	Integrase Inhibitor (N=xxx)			Protease Inhibitor (N=xxx)			Adjusted Incidence	
	N of event	Person- years	IR per 100 p-y	N of event	Person- years	IR per 100 p-y)	rate ratio (95% CI)	p- value
Composite Primary endpoint								

All observed endpoint will be considered in the analysis. In this analysis, the entire follow-up will be considered (i.e. follow-up began at baseline and continued until the end of the study, study discontinuation, loss to follow-up; whichever occurs first). The incidence rates will be calculated by the total number of events from baseline to the end of the study divided by the total number of person-years. The incidence rates will be compared between the treatment groups (Integrase inhibitor versus Protease inhibitor) with a Poisson regression model adjusted for stratification factor. The incidence rates ratio and the associated 95% confidence interval will be calculated.

TABLE 3. HIV-RNA VIRAL LOAD <50 COPIES/ML AT WEEK 24, 36 AND 48

		Integrase Inhibitor		Protease Inhibitor		Adjusted OR	adjusted difference
		N=XXX		N=XXX		(95% CI)	(95% CI)
		N	% (95% CI)	N	% (95% CI)		
W24	HIV-RNA < 50 copies/mL						
	HIV-RNA ≥ 50 copies/mL						
	Data in window not below 50 copies/mL						
	Discontinued for lack of efficacy						
	Change in background therapy						
	No virologic data						
	Discontinuation due to AE/SAE						
	Discontinuation due for other reason						
	On study but missing data in window						
W36	HIV-RNA < 50 copies/mL						
	HIV-RNA ≥ 50 copies/mL						
	Data in window not below 50 copies/mL						
	Discontinued for lack of efficacy						
	Change in background therapy						
	No virologic data						
	Discontinuation due to AE/SAE						
	Discontinuation due for other reason						
	On study but missing data in window						
W48	HIV-RNA < 50 copies/mL						
	HIV-RNA ≥ 50 copies/mL						
	Data in window not below 50 copies/mL						
	Discontinued for lack of efficacy						
	Change in background therapy						
	No virologic data						
	Discontinuation due to AE/SAE						
	Discontinuation due for other reason						
	On study but missing data in window						

TABLE 4. OTHER SECONDARY EFFICACY ENDPOINTS

	Integrase Inhibitor	Protease Inhibitor	Adjusted Hazard ratio	P-value
	N=XXX	N=XXX		
Kaplan-Meier estimate of percentage of patients with CD4>200/ μ L, n (%)				
Kaplan-Meier estimate of median (95% CI) time to reach CD4>200/ μ L				
Kaplan Meier estimate of incidence of IRIS, n (%)				
Kaplan-Meier estimate of Incidence of hospitalisations, , n (%)				
Kaplan-Meier estimate of median (95% CI) duration of hospitalisation				

TABLE 5: EVOLUTION OF CD4 CELL COUNT <200/ μ L AND <350 AT WEEK 4, 8, 12, 24, 36 AND 48

Week	CD4 cell count <200/ μ L			CD4 cell count <350/ μ L		
	Integrase Inhibitor	Protease Inhibitor	P-value between groups	Integrase Inhibitor	Protease Inhibitor	P-value between groups
	n/N (%)	n/N (%)		n/N (%)	n/N (%)	
0						
4						
8						
12						
24						
36						
48						
RR (95% CI) from baseline to W4						
RR (95% CI) from baseline to W8						
RR (95% CI) from baseline to W12						
RR (95% CI) from baseline to W24						
RR (95% CI) from baseline to W36						
RR (95% CI) from baseline to W48						

TABLE 6: EVOLUTION OF CD4/CD8 RATIO AT WEEK 4, 8, 12, 24, 36 AND 48

Week	CD4/CD8 ratio		
	Integrase Inhibitor	Protease Inhibitor	P-value between groups
	Mean (SD)	Mean (SD)	
0			
4			
8			
12			
24			
36			
48			
Mean (95% CI) difference from baseline to week 4			
Mean (95% CI) difference from baseline to week 8			
Mean (95% CI) difference from baseline to week 12			
Mean (95% CI) difference from baseline to week 24			
Mean (95% CI) difference from baseline to week 36			
Mean (95% CI) difference from baseline to week 48			

TABLE 7: SAFETY

	Integrase inhibitor (N=XXX) Person-Year (P-Y): XXX.X			Protease inhibitor (N=XXX) Person-Year (P-Y): XXX.X			P-value
	N of events	N of pts (%)	Incidence rate/100 p-y	N of events	N of pts (%)	Incidence rate/100 p-y	
Any adverse events (AEs : grade ≥2)							
Grade 2							
Grade 3							
Grade 4							
Grade unknown							
Grade 3 or 4 AE							
Drug related AEs							
Drug related grade 3/4 AEs							
dress syndrom (rash)							
IRIS							
IRIS-Kaposis sarcoma							
PML-IRIS requiring hospitalisation							
progressive rash							
transaminitis							
worsening symptoms of Progressive multifocal leukoencephalopathy							
....							
....							
AE leading to the study drugs interruption							
Serious adverse events (SAE)							
Laboratory toxicities							
Death							

TABLE 8. OTHER SECONDARY ENDPOINTS

	Integrase Inhibitor	Protease Inhibitor	Adjusted OR	P-value
	N=XXX	N=XXX	(95% CI)	
Percentage of patients with HIV drug resistance mutations among those with virological failure				
Proportion of patients with ART treatment changes due to toxicities and/or DDI with ART, and/or IRIS through week 48 - due to toxicities - due to DDI - due to IRIS				
Proportion of patients with with health care resource use, including total inpatient days and emergency room visits through week 48				
Proportion of patients with discontinuation or modification of study medication due to insufficient virological response or resistance mutations development before week 48 - for insufficient virological response - resistance mutations development				
Proportion of patients for whom there is a difference in the list of mutations (Stanford list last available version) detected by deep sequencing compared with those detected by population sequencing				

TABLE 9: EVOLUTION OF QUALITY OF LIFE (HEALTH STATUS SCORE) AND HIV SYMPTOMS INDEX

Week	QOL : health status score			HIV Symptoms index score		
	Integrase Inhibitor	Protease Inhibitor	P-value between groups	Integrase Inhibitor	Protease Inhibitor	P-value between groups
	Mean (SD)	Mean (SD)		Mean (SD)	Mean (SD)	
0						
4						
8						
12						
24						
36						
48						
Mean (SD) from baseline to W4						
Mean (SD) from baseline to W8						
Mean (SD) from baseline to W12						
Mean (SD) from baseline to W24						
Mean (SD) from baseline to W36						
Mean (SD) from baseline to W48						

TABLE 10: QUALITY OF LIFE DIMENSIONS: MOBILITY AND SELF- CARE

Week	Mobility			Self- care		
	Integrase Inhibitor	Protease Inhibitor	P-value between groups	Integrase Inhibitor	Protease Inhibitor	P-value between groups
0 1=no problems, 2=some problems, 3=extreme problems	n/N (%)	n/N (%)		n/N (%)	n/N (%)	
4 1=no problems, 2=some problems, 3=extreme problems						
8 1=no problems, 2=some problems, 3=extreme problems						
12 1=no problems, 2=some problems, 3=extreme problems						
24 1=no problems, 2=some problems, 3=extreme problems						
36 1=no problems, 2=some problems, 3=extreme problems						
48 1=no problems, 2=some problems, 3=extreme problems						
RR (95% CI) from baseline to W4						
RR (95% CI) from baseline to W8						
RR (95% CI) from baseline to W12						
RR (95% CI) from baseline to W24						
RR (95% CI) from baseline to W36						
RR (95% CI) from baseline to W48						

TABLE 11: QUALITY OF LIFE DIMENSIONS: USUAL ACTIVITIES AND PAIN/DISCOMFORT

Week	Usual activities			Pain/discomfort		
	Integrase Inhibitor	Protease Inhibitor	P-value between groups	Integrase Inhibitor	Protease Inhibitor	P-value between groups
0 1=no problems, 2=some problems, 3=extreme problems	n/N (%)	n/N (%)		n/N (%)	n/N (%)	
4 1=no problems, 2=some problems, 3=extreme problems						
8 1=no problems, 2=some problems, 3=extreme problems						
12 1=no problems, 2=some problems, 3=extreme problems						
24 1=no problems, 2=some problems, 3=extreme problems						
36 1=no problems, 2=some problems, 3=extreme problems						
48 1=no problems, 2=some problems, 3=extreme problems						
RR (95% CI) from baseline to W4						
RR (95% CI) from baseline to W8						
RR (95% CI) from baseline to W12						
RR (95% CI) from baseline to W24						
RR (95% CI) from baseline to W36						
RR (95% CI) from baseline to W48						

TABLE 12: QUALITY OF LIFE DIMENSIONS: ANXIETY/DEPRESSION

Week	Anxiety/depression		
	Integrase Inhibitor	Protease Inhibitor	P-value between groups
n/N (%)	n/N (%)		
0 1=no problems, 2=some problems, 3=extreme problems			
4 1=no problems, 2=some problems, 3=extreme problems			
8 1=no problems, 2=some problems, 3=extreme problems			
12 1=no problems, 2=some problems, 3=extreme problems			
24 1=no problems, 2=some problems, 3=extreme problems			
36 1=no problems, 2=some problems, 3=extreme problems			
48 1=no problems, 2=some problems, 3=extreme problems			
RR (95% CI) from baseline to W4			
RR (95% CI) from baseline to W8			
RR (95% CI) from baseline to W12			
RR (95% CI) from baseline to W24			
RR (95% CI) from baseline to W36			
RR (95% CI) from baseline to W48			

TABLE 13. HIV-RNA VIRAL LOAD <50 COPIES/mL AT WEEK 4, 8 AND 12

		Integrase Inhibitor		Protease Inhibitor		Adjusted OR (95% CI)	adjusted difference (95% CI)		
		N=XXX		N=XXX					
		N	% (95% CI)	N	% (95% CI)				
W4	HIV-RNA < 50 copies/mL								
	HIV-RNA ≥ 50 copies/mL								
	Data in window not below 50 copies/mL								
	Discontinued for lack of efficacy								
	Change in background therapy								
	No virologic data								
	Discontinuation due to AE/SAE								
	Discontinuation due for other reason								
	On study but missing data in window								
W8	HIV-RNA < 50 copies/mL								
	HIV-RNA ≥ 50 copies/mL								
	Data in window not below 50 copies/mL								
	Discontinued for lack of efficacy								
	Change in background therapy								
	No virologic data								
	Discontinuation due to AE/SAE								
	Discontinuation due for other reason								
	On study but missing data in window								
W12	HIV-RNA < 50 copies/mL								
	HIV-RNA ≥ 50 copies/mL								
	Data in window not below 50 copies/mL								
	Discontinued for lack of efficacy								
	Change in background therapy								
	No virologic data								
	Discontinuation due to AE/SAE								
	Discontinuation due for other reason								
	On study but missing data in window								

TABLE 14: ADHERENCE TO STUDY MEDICATION OVER TIME

		Randomisation			
		Integrase inhibitor N=xxx		Protease inhibitor N=xxx	
		N	%	N	%
WK12	How often has patient taken medication?	All the time			
		Most of the time			
		About half the time			
		Very few times			
		None			
		Total			
WK24	How often has patient taken medication?	All the time			
		Most of the time			
		About half the time			
		Very few times			
		None			
		Total			
WK36	How often has patient taken medication?	All the time			
		Most of the time			
		About half the time			
		Very few times			
		None			
		Total			
WK48	How often has patient taken medication?	All the time			
		Most of the time			
		About half the time			
		Very few times			
		None			
		Total			

TABLE 15: CHANGE FROM BASELINE IN LABORATORY RESULTS

Laboratory parameters	Week	Integrase Inhibitor N=xxx		Protease Inhibitor N=xxx		P-value between groups
		N	Mean (SE)	N	Mean (SE)	
Red blood cells (10¹²/L)	0					
	4					
	8					
	12					
	24					
	36					
	48					
	Mean (SE) difference from baseline to week 48					
White blood cells (10¹²/L)	0					
	4					
	8					
	12					
	24					
	36					
	48					
	Mean (SE) difference from baseline to week 48					
Platelet counts (10⁹/L)	0					
	4					
	8					
	12					
	24					
	36					
	48					
	Mean (SE) difference from baseline to week 48					
Haemoglobin (g/dL)	0					
	4					

	8					
	12					
	24					
	36					
	48					
	Mean (SE) difference from baseline to week					
	48					
Hematocrit (%)	0					
	4					
	8					
	12					
	24					
	36					
	48					
	Mean (SE) difference from baseline to week					
	48					
MVC (fl)	0					
	4					
	8					
	12					
	24					
	36					
	48					
	Mean (SE) difference from baseline to week					
	48					
MCH (pg)	0					
	4					
	8					
	12					
	24					
	36					
	48					

	Mean (SE) difference from baseline to week 48					
Neutrophils (10⁹/L)	0					
	4					
	8					
	12					
	24					
	36					
	48					
	Mean (SE) difference from baseline to week 48					
Lymphocytes (10⁹/L)	0					
	4					
	8					
	12					
	24					
	36					
	48					
	Mean (SE) difference from baseline to week 48					
Monocytes (10⁹/L)	0					
	4					
	8					
	12					
	24					
	36					
	48					
	Mean (SE) difference from baseline to week 48					
Eosinophils (10⁹/L)	0					
	4					
	8					

	12					
	24					
	36					
	48					
	Mean (SE) difference from baseline to week 48					
Basophils (10⁹/L)	0					
	4					
	8					
	12					
	24					
	36					
	48					
	Mean (SE) difference from baseline to week 48					
Potassium (mmol/L)	0					
	4					
	8					
	12					
	24					
	36					
	48					
	Mean (SE) difference from baseline to week 48					
Total Protein (g/L)	0					
	4					
	8					
	12					
	24					
	36					
	48					
	Mean (SE) difference from baseline to week 48					

Sodium (mmol/L)	0				
	4				
	8				
	12				
	24				
	36				
	48				
	Mean (SE) difference from baseline to week 48				
ALT (U/L)	0				
	4				
	8				
	12				
	24				
	36				
	48				
	Mean (SE) difference from baseline to week 48				
Total bilirubin (umol/L)	0				
	4				
	8				
	12				
	24				
	36				
	48				
	Mean (SE) difference from baseline to week 48				
Indirect bilirubin (umol/L)	0				
	4				
	8				
	12				
	24				
	36				

	48					
	Mean (SE) difference from baseline to week 48					
AST (U/L)	0					
	4					
	8					
	12					
	24					
	36					
	48					
	Mean (SE) difference from baseline to week 48					
Albumin (g/L)	0					
	4					
	8					
	12					
	24					
	36					
	48					
	Mean (SE) difference from baseline to week 48					
Creatinine (umol/L)	0					
	4					
	8					
	12					
	24					
	36					
	48					
	Mean (SE) difference from baseline to week 48					
Creatinine clearance (mL/min)	0					

	4					
	8					
	12					
